## 8.0 TRIAL FLOW CHART

STUDY FLOW CHART – ARM A	Treatment Cycle/Title: Screening (Visit 1)	Treatment Cycles 										Post-treatment		
		1&4				2&5			3&6			Discon	Safety Follow-up	Follow Up Visits
		D1	D8	D15	D22	D1	D8	D15	D1	D8	D15			
Scheduling Window (Days) ± 2 :												At time of Discon	30 days post discon	Every 8 weeks post discon
Informed Consent	x													
Inclusion/Exclusion Criteria	x													
Demographics and Medical History	x													
Prior and Concomitant Medication Review	x	x-----x								x	x			
Post-study anticancer therapy status													x	x 
Review Adverse Events		x-----x								x	x		x 	
Physical Examination	x	x 	x 	x 	x 	x			x			x	x	
Vital Signs and Weight	x	x-----on all days with physical exam or infusion-----x								x	x			
ECOG Performance Status	X	x 	x 	x 	x 	x 			x			x	x	
Pregnancy Test – Urine or Serum β-HCG	X													
PT/INR and aPTT	X	x 				x			x					
CBC with Differential	x	x 	x	x	x	x	x	x	x	x	x	x	x	

STUDY FLOW CHART – ARM A	Treatment Cycle/Title: Screening (Visit 1)	Treatment Cycles 									Post-treatment			
		1&4			2&5			3&6			Discon	Safety Follow-up	Follow Up Visits	
		D1	D8	D15	D22	D1	D8	D15	D1	D8	D15			
Scheduling Window (Days) ± 2 :												At time of Discon	30 days post discon	Every 8 weeks post discon
Chemistry 	x	x 	x	x	X	x	x	x	x	x	x	x	x	
EBV PCR	x													
Urinalysis	x													
T3, FT4 and TSH	x	x 				x 			x 			x	x	
Tumor Imaging 	x 					x 			x 					
mSWAT and photograph of skin involvement 	x 	x 				x 			x 					
Archival/Newly Obtained Tissue Collection	x 								x 					
Correlative Studies Blood Collection		x	x 	x 		x			x			x		
Pharmacokinetics (PKs) 		x	x 	x 										
Pralatrexate IV push		x	x	x		x	x	x	x	x	x			
Pembrolizumab Infusion		x 			X			x		x				

X After cycle 6, cycle 7 will follow the calendar for cycle 1&4, cycle 8 will follow the calendar for cycle 2&5, cycle 9 will follow the calendar for cycle 3&6 etcetera

X Physical exam will be performed weekly ONLY during cycle 1. Physical Exam will be performed only at D1 of each subsequent cycle beyond cycle 1.

X ECOG will be performed weekly ONLY during cycle 1. ECOG will be performed only at D1 of each subsequent cycle beyond cycle 1.

X CT/PET or CT will be performed at screening within 4 weeks from treatment start date and after cycle 2; then it will be repeated every 3 to 4 cycles at the discretion of the treating physician.

X mSWAT and standardized photographs of skin involvement are strongly recommended at screening or cycle 1 day 1 not at both timepoints. mSWAT is required to be performed after cycle 2 and then it will be repeated every 3 to 4 cycles at the discretion of the treating physician. mSWAT will be performed along with CT/PET or CT evaluation.

X Blood samples and tissue collection should be obtained in the screening phase of the study

X Tissue collection of the tumor lesion (including possible FNA or ultrasound when indicated per standard care) should be obtained, if possible, at screening or within Cycle 1 (please refer to section [6.1.1: Subject Inclusion Criteria](#) number 7). An optional biopsy may be performed post Cycle 3 or 4.

X Pharmacokinetics (PKs) blood draws are only for patients at UVA. See [section 9.1.7.3](#) for details.

X Pembrolizumab will be administered every 3 weeks (Q3W). In Arm A, pembrolizumab administration will be started on day 1 of cycle 1 as described in section 5.2.1.

X For cycle 1 day 1, laboratory screening tests can be considered valid for treatment on cycle 1 day 1 as long as they are performed within the screening laboratory test window (10 days). After Cycle 1, pre-dose laboratory procedures can be conducted up to 72 hours prior to dosing.

X Pharmacokinetics (PKs) and correlative study blood draws at Days 8 and 15 in a cycle are only for Cycle 1 (not cycles 4, 7, etc.)

X For subjects who have an allogeneic SCT within 24 months of last study treatment, transplant parameters will be collected and specific events will be collected for 18 months from the date of the allogeneic transplant to include graft-versus-host-disease (acute and/or chronic), veno-occlusive disease, febrile syndrome (a steroid-requiring febrile illness without an infectious cause), and encephalitis, for all grades, and regardless of relationship to study drug. Additional medically important adverse events post-allogeneic SCT may be submitted at the Investigator's discretion.

X See table in [section 9.1.7](#) for list of tests to include (not just the comprehensive metabolic panel)

X Thyroid blood tests are only required every other cycle (e.g. day 1 only for odd cycles)

X After 30 day safety visit, only new SAEs considered related to study intervention need to be collected and assessments (as applicable) may be by phone or videoconference. Active AEs at the time of 30 day safety visit should be followed through resolution or stability.

STUDY FLOW CHART – ARM B		Treatment Cycles 												Post-treatment		
Treatment Cycle/Title:		Screening (Visit 1)	1&4				2&5				3&6			Discon	Safety Follow-up	Follow Up Visits
Scheduling Window (Days) ± 2 :			D1	D8	D15	D22	D1	D8	D15	D22	D1	D8	D15			
Informed Consent	X															
Inclusion/Exclusion Criteria	X															
Demographics and Medical History	X															
Prior and Concomitant Medication Review	X		x-----x										x	x		
Post-study anticancer therapy status															x	x 
Review Adverse Events			x-----x										x	x	x 	
Physical Examination	X	x 	x 	x 			x				x			x	x	
Vital Signs and Weight	X		x-----on all days with physical exam or infusion----x										x	x		
ECOG Performance Status	X	x 	x 	x 		x				x			x	x		
Pregnancy Test – Urine or Serum β-HCG	X															
PT/INR and aPTT	X	x 				x				x						
CBC with Differential	X	x 	x	x	x 	x	x	x	x	x	x	x	x	x	x	
Chemistry 	X	x 	x	x		x	x	x	x 	x	x	x	x	x	x	
EBV PCR	x															

STUDY FLOW CHART – ARM B		Treatment Cycles 												Post-treatment		
Treatment Cycle/Title:		Screening (Visit 1)	1&4				2&5				3&6			Discon	Safety Follow-up	Follow Up Visits
Scheduling Window (Days) ± 2 :			D1	D8	D15	D22	D1	D8	D15	D22	D1	D8	D15	At time of Discon	30 days post discon	Every 8 weeks post discon
Urinalysis	x															
T3, FT4 and TSH	x	x  15					x 				x 			x	x	
Tumor Imaging 	x 						x 				x 					
mSWAT and photograph of skin involvement 	x 	x 					x 				x 					
Archival/Newly Obtained Tissue Collection	x 										x 					
Correlative Studies Blood Collection		x	x 	x 		x				x			x			
Pharmacokinetics (PKs) 		x 	x 	x 												
Pralatrexate		x	x	x		x	x	x		x	x	x				
Decitabine		x 				x 				x 						
Pembrolizumab			x 			x			x			x				

X After cycle 6, cycle 7 will follow the calendar for cycle 1&4, cycle 8 will follow the calendar for cycle 2&5, cycle 9 will follow the calendar for cycle 3&6 etcetera.

X Physical exam will be performed weekly only during cycle 1. It will be performed ONLY at D1 of each subsequent cycle beyond cycle 1.

X ECOG should be only performed at D1 of each cycle beyond cycle 4.

X CT/PET or CT will be performed at screening within 4 weeks from treatment start date and after cycle 2; then it will be repeated every 3 to 4 cycles at the discretion of the treating physician.

X mSWAT and standardized photographs of skin involvement are strongly recommended at screening or cycle 1 day 1 not at both timepoints. mSWAT is required to be performed after cycle 2 and then it will be repeated every 3 to 4 cycles at the discretion of the treating physician. mSWAT will be performed along with CT/PET or CT evaluation

X Blood samples and tissue collection should be obtained in the screening phase of the study.

X Tissue collection of the tumor lesion (including possible FNA or ultrasound when indicated per standard care) should be obtained, if possible, at screening or within Cycle 1 (please refer to section [6.1.1: Subject Inclusion Criteria](#) number 7). An optional biopsy may be performed post Cycle 3 or 4.

X The pharmacokinetics (PKs) blood draw are only for patients at UVA. See [section 9.1.7.3](#) for details. .

X Cycle 1 only. Additional pharmacokinetics sample (only for patients at UVA) will be obtained at day 5 to determine drug steady state.

X Decitabine will be given from day 1 to day 5 (or day 3, depending on dose level) of each cycle as described in section 5.2.3

X Pembrolizumab will be administered every 3 weeks (Q3W). In Arm B, pembrolizumab administration will be started on day 8 of cycle 1 as described in section 5.2.1.

X For cycle 1 day 1, laboratory screening tests can be considered valid for treatment on cycle 1 day 1 as long as they are performed within the screening laboratory test window (10 days). After Cycle 1, pre-dose laboratory procedures can be conducted up to 72 hours prior to dosing.

X Pharmacokinetics (PKs) and correlative study blood draws at Days 8 and 15 in a cycle are only for Cycle 1 (not cycles 4, 7, etc.)

X For subjects who have an allogeneic SCT within 24 months of last study treatment, transplant parameters will be collected and specific events will be collected for 18 months from the date of the allogeneic transplant to include graft-versus-host-disease (acute and/or chronic), veno-occlusive disease, febrile syndrome (a steroid-requiring febrile illness without an infectious cause), and encephalitis, for all grades, and regardless of relationship to study drug. Additional medically important adverse events post-allogeneic SCT may be submitted at the Investigator's discretion.

X Thyroid blood tests are only required every other cycle (e.g. day 1 only for odd cycles)

X After cycle 2, the day 22 CBC with differential is not required (e.g. not for cycles 5, 8, etc.)

X After 30 day safety visit, only new SAEs considered related to study intervention need to be collected and assessments (as applicable) may be by phone or videoconference. Active AEs at the time of 30 day safety visit should be followed through resolution or stability.

X See table in [section 9.1.7](#) for list of tests to include (not just the comprehensive metabolic panel)

X CBC with differential at Day 22 is for cycle 1 only (e.g. not for cycles 4, 7, etc)

STUDY FLOW CHART – ARM C	Treatment Cycle/Title:	Treatment Cycles 								Post-treatment			
		Screening (Visit 1)	1&4				2&5		3 &6		Discon	Safety Follow-up	Follow Up Visits
			D1	D8	D15	D22	D1	D22	D1	D15			
Scheduling Window (Days) ± 2 :											At time of discon	30 days post discon	Every 8 weeks post discon
Informed Consent	x												
Inclusion/Exclusion Criteria	x												
Demographics and Medical History	x												
Prior and Concomitant Medication Review	x		x-----x							x		x	x
Post-study anticancer therapy status											x		x 
Review Adverse Events			x-----x							x		x	x 
Physical Examination	x	x 	x 				x		x		x	x	
Vital Signs and Weight	x		x-on all days with physical exam or infusion-x							x		x	
ECOG Performance Status	x	x 	x				x		x		x	x	
Pregnancy Test – Urine or Serum β-HCG	x												
PT/INR and aPTT	x	x 					x		x				
CBC with Differential	x	x 	x	X 	x 		x	x 	x	x	x	x	
Chemistry 	x	x 	x	X 			x	x	x	x	x	x	
EBV PCR	x												

STUDY FLOW CHART – ARM C		Treatment Cycles 								Post-treatment		
		Screening (Visit 1)	1&4			2&5		3 &6		Discon	Safety Follow-up	Follow Up Visits
Scheduling Window (Days) ± 2 :			D1	D8	D15	D22	D1	D22	D1	D15	At time of discon	30 days post discon
Urinalysis	x											
T3, FT4 and TSH	x	x 					x 		x 		x	x
Tumor Imaging 	x 						x 		x 			
mSWAT and Photograph of skin involvement 	x 	x 					x 		x 			
Archival/Newly Obtained Tissue Collection	x 								x 			
Correlative Studies Blood Collection		x	x 	x 		x		x		x		
Pharmacokinetics (PKs) 		x 										
Decitabine		x 					x 		x 			
Pembrolizumab			x 				x 	x 		x 		

X After cycle 6, cycle 7 will follow the calendar for cycle 1&4, cycle 8 will follow the calendar for cycle 2&5, cycle 9 will follow the calendar for cycle 3&6 etcetera

X Physical exam should be performed ONLY at D1 of each cycle beyond cycle 4

X ECOG should be only performed at D1 of each cycle beyond cycle 4

X CT/PET or CT will be performed at screening within 4 weeks from treatment start date and after cycle 2; then it will be repeated every 3 to 4 cycles at the discretion of the treating physician.

X mSWAT and standardized photographs of skin involvement are strongly recommended at screening or cycle 1 day 1 not at both timepoints. mSWAT is required to be performed after cycle 2 and then it will be repeated every 3 to 4 cycles at the discretion of the treating physician. mSWAT will be performed along with CT/PET or CT evaluation.

X Blood samples and tissue collection should be obtained in the screening phase of the study.

X Tissue collection of the tumor lesion (including possible FNA or ultrasound when indicated per standard care) should be obtained, if possible, at screening or within Cycle 1 (please refer to section [6.1.1: Subject Inclusion Criteria](#) number 7). An optional biopsy may be performed post Cycle 3 or 4.

X The pharmacokinetics (PKs) blood draw are only for patients at UVA. See [section 9.1.7.3](#) for details. X Cycle 1 only. Additional pharmacokinetics sample (only for patients at UVA) will be obtained on the final day (in Cycle 1) of scheduled treatment for the participant to determine drug steady state. See [section 9.1.7.3](#) for details.

X Decitabine will be given from day 1 to day 5 (or day 3, depending on dose level) of each cycle as described in section 5.2.3

X Pembrolizumab will be administered every 3 weeks (Q3W). In Arm C, pembrolizumab administration will be started on day 8 of cycle 1 as described in section 5.2.1.

X For cycle 1 day 1, laboratory screening tests can be considered valid for treatment on cycle 1 day 1 as long as they are performed within the screening laboratory test window (10 days). After Cycle 1, pre-dose laboratory procedures can be conducted up to 72 hours prior to dosing.

X Correlative study blood draws at Days 8 and 15 in a cycle are only for Cycle 1 (not cycles 4, 7, etc.). Labs (CBC with differential and Chemistry) on day 15 are for cycle 1 only.

X For subjects who have an allogeneic SCT within 24 months of last study treatment, transplant parameters will be collected and specific events will be collected for 18 months from the date of the allogeneic transplant to include graft-versus-host-disease (acute and/or chronic), veno-occlusive disease, febrile syndrome (a steroid-requiring febrile illness without an infectious cause), and encephalitis, for all grades, and regardless of relationship to study drug. Additional medically important adverse events post-allogeneic SCT may be submitted at the Investigator's discretion.

X After cycle 2, the day 22 CBC with differential is not required (e.g. not for cycles 5, 8, etc.)

X Thyroid blood tests are only required every other cycle (e.g. day 1 only for odd cycles)

X After 30 day safety visit, only new SAEs considered related to study intervention need to be collected and assessments (as applicable) may be by phone or videoconference. Active AEs at the time of 30 day safety visit should be followed through resolution or stability.

X See table in [section 9.1.7](#) for list of tests to include (not just the comprehensive metabolic panel)

X CBC with differential at Day 22 is for cycle 1 only (e.g. not for cycles 4, 7, etc)

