### 3.2 Secondary Objectives

- Describe the anti-tumor activity of the combinations of pembrolizumab and pralatrexate (Arm A), pralatrexate, decitabine and pembrolizumab (Arm B), and decitabine and pembrolizumab (Arm C) in patients with relapsed/refractory PTCL and CTCL.
- Evaluate the efficacy, as determined by the overall response rate (ORR), progression free survival (PFS), and duration of response (DOR), of the study population receiving the combinations of pembrolizumab and pralatrexate (Arm A), pralatrexate, decitabine and pembrolizumab (Arm B), and decitabine and pembrolizumab (Arm C) in patients with relapsed/refractory PTCL and CTCL.
- Evaluate pharmacodynamic markers of drug effect in paired tissue biopsies (pre- and post-treatment).
- Establish pharmacokinetic profile for pembrolizumab when administered with pralatrexate (Arm A), with decitabine (Arm C) and when given as a combination (Arm B) during cycle 1 only.
- Obtain additional information regarding adverse events within the selected dose range.

- Estimate the OS, PFS of the combination in patients with relapsed/refractory PTCL and CTCL.
- Estimate the DOR of patients with relapsed/refractory PTCL and CTCL on study.
- Identify potential biomarkers of response to treatment.

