#### **5.6 Biomarker Research**

The trial will aim to identify biomarkers that may correlate with clinical activity of pembrolizumab through the following steps:

- Analyze the changes on T cell repertoire in peripheral blood and primary tumor samples as a function of treatment with pralatrexate, decitabine and pembrolizumab and assess the contribution of epigenetic priming with decitabine in patients receiving treatment with pembrolizumab and pralatrexate.

Standard flow cytometry to assess CD3, CD4, CD8, CD25, CD80, PD1, PD-L1, PD-L2 and Foxp3 will be performed in peripheral blood mononuclear cells. In addition, peripheral blood T lymphocytes will be analyzed by flow cytometry for CD45 RA, CCR7, CD62L to understand changes in the T cell repertoire. Correlation in between changes and response to treatment will be made.

Paraffin embedded primary tumor samples will be obtained pre- and post-treatment as defined below and OpalMultiplexing “MANTRA” will be performed. MANTRA is a tissue evaluation technique, which uses a fluorescent signal amplification probe to permit serial immunohistochemistry and compared to conventional immunohistochemistry permits multiplex detection. Opal Multiplexing MANTRA will be used to determine changes in the microenvironment (TILs, NK-cell and antigen-presenting cells) as a function of treatment. The following set of 6 markers will be analyzed on each tissue biopsy: CD3, CD7, CD4, CD8, PGM1, IDO; CD3, CD7, CD4, CD8, CD20, FOXP3; CD3, CD7, CD4, CD8, PD-1, PD-L1; CD3, CD7, CD4, CD8, CD56, Granzyme B.

- Elucidate the immune modulatory effect of pralatrexate and decitabine and identify biomarker of response accounting for heterogeneity and dynamic changes.

Gene expression profiling (GEP) analysis will be obtained on primary tumor samples pre- and post-treatment. Changes of gene expression profiling as a function of treatment with pralatrexate and decitabine will be analyzed. Specific attention will be placed on defined gene-signature already described and predictive of response to pembrolizumab (e.g. interferon- $\gamma$ -related genes including CXCL9, CXCL10, IDO1, IFNG, HLA-DRA, STAT1). Additional signature associated with clinical outcome will be investigated.

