Genome wide methylation analysis will be performed to identify and quantify changes in methylation pre- and post-treatment. Specific attention will be placed on decitabine contribution in de-repressing and inducing transcription of multiple DNA hypermethylated human endogenous retrovirus (HERV) genes triggering a type I interferon-response.

GEP and methylation wide methylation profiling will be analyzed, and correlation will be made to identify biomarkers of response. The data gathered from the GEP and genome wide methylation will be used to create an algorithm of regulatory networks within PTCLs. The analysis of these data will provide information on etiology of PTCLs and will suggest possible targetable oncogenic pathways.

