#### 6.1.1 Subject Inclusion Criteria

In order to be eligible for participation in this trial, the subject must:

1. Be willing and able to provide written informed consent/assent for the trial.
2. Be  $\geq 18$  years of age on day of signing informed consent.
3. Have measurable disease as defined by the Lugano Criteria for PTCL (Cheson et al., 2014) and by the Global Response Score for CTCL (Olsen et al., 2011).
4. Patient must have histologically confirmed relapsed or refractory Peripheral T-cell lymphoma (PTCL) or cutaneous T-cell Lymphoma (CTCL) as per WHO criteria and TNMB classification and staging.
5. There is no upper limit for the number of prior therapies. Patient may have relapsed after prior autologous stem cell transplant.
6. Patients who had prior treatment for their disease, as long as there is radiographic evidence of refractory or relapsed disease and the patient meets all other clinical and laboratory criteria for study treatment.
7. Be willing to provide tissue from a newly obtained core or excisional biopsy of a tumor lesion. Be willing to provide FNA of a tumor lesion. *Newly-obtained is defined as a specimen obtained up to 6 weeks (42 days) prior to initiation of treatment on Day 1. Subjects for whom newly obtained samples cannot be provided (e.g. inaccessible or subject safety concern) may submit an archived specimen only upon agreement from the Sponsor.*
8. Have a performance status of 0 or 1 on the ECOG Performance Scale.
9. Demonstrate adequate organ function as defined in Table 6, all screening labs should be performed within 10 days of treatment initiation.

Table 6: Adequate Organ Function Laboratory Values.

System	Laboratory Value
Hematological	
Absolute neutrophil count (ANC)	$\geq 1,000 / \text{mcL}$
Platelets	$\geq 75,000 / \text{mcL}$
Hemoglobin	$\geq 9 \text{ g/dL}$ or $\geq 5.6 \text{ mmol/L}$ without transfusion or EPO dependency (within 7 days of assessment)
Renal	
Serum creatinine OR Measured or calculated a creatinine clearance (GFR can also be used in place of creatinine or CrCl)	$\leq 1.5 \times \text{upper limit of normal (ULN)}$ OR $\geq 60 \text{ mL/min}$ for subject with creatinine levels $> 1.5 \times$ institutional ULN
Hepatic	
Serum total bilirubin	$\leq 1.5 \times \text{ULN}$ OR Direct bilirubin $\leq \text{ULN}$ for subjects with total bilirubin levels $> 1.5 \times \text{ULN}$

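### Footnote 7 of all three flow charts lets the first tumour sample be taken after dosing has begun, contradicting footnote 6, inclusion criterion 7 and the paired pre/post biopsy objective

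*Protocol*

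**What the plan says.** **The footnotes.** In the Section 8.0 flow charts, footnote 7 to the tissue-collection row states that tissue from the tumour lesion "should be obtained, if possible, at screening or within Cycle 1" and refers the reader to inclusion criterion 7. It then adds: "An optional biopsy may be performed post Cycle 3 or 4". The wording is the same for Arms A, B and C. Footnote 6, attached to the screening cell of the same row, reads "Blood samples and tissue collection should be obtained in the screening phase of the study".

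**Eligibility.** Section 6.1.1, criterion 7, asks that the subject be willing to give fresh tissue. It states: "Newly-obtained is defined as a specimen obtained up to 6 weeks (42 days) prior to initiation of treatment on Day 1". Where fresh tissue cannot be had, subjects "may submit an archived specimen only upon agreement from the Sponsor".

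**What the tissue is for.** Section 3.2 lists as a secondary objective "Evaluate pharmacodynamic markers of drug effect in paired tissue biopsies (pre- and post-treatment". Section 5.6 says of the multiplex staining that "Paraffin embedded primary tumor samples will be obtained pre- and post-treatment as defined below", and of methylation that "Genome wide methylation analysis will be performed to identify and quantify changes in methylation pre- and post-treatment". Gene expression is treated the same way there, and Section 9.1.7.2 repeats all three.

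**When drug starts.** A cycle is 28 days (Section 5.1). By Sections 5.2.1 to 5.2.3, Day 1 of Cycle 1 brings pembrolizumab and pralatrexate in Arm A, decitabine and pralatrexate in Arm B, and decitabine in Arm C. Pembrolizumab follows on Day 8 in Arms B and C.

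**The concern.** The first sample in footnote 7 is one half of a pair, and its only use in the paired objective is to show the tumour before treatment. If it may be taken at any time in Cycle 1, a site can comply with footnote 7 and still deliver tissue that has already met study drug.

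The biology in the protocol makes this more than a formality. Sections 4.2.2 and 4.3.3 describe decitabine as an agent that demethylates DNA and alters expression of the related genes. Those are the quantities that the methylation and expression analyses are meant to track. The exploratory objective in Section 3.3 also wants the contribution of decitabine priming, and that contribution may already be present in a Cycle 1 sample from Arm B or C.

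The loss is permanent. If no pre-dose tissue was taken, later analysis cannot supply it. Pairs may also be scarce: accrual is capped at 38 across three arms (Section 10.4) and the second biopsy is optional.

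**Working it through.** No computed figure in the protocol bears on this point. The check sets the timing statements against the dosing calendar and then asks what a post-dose first sample does to a paired change.

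**Step 1. Which sample does footnote 7 describe?** The other biopsy it mentions comes after Cycle 3 or 4, so its first sentence must describe the earlier member of the pair. The Section 12.0 change log (09/23/2020 to 11/03/2020) supports this: it says that footnote 7 was clarified for a pretreatment biopsy and an optional post-treatment one.

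**Step 2. Which days of Cycle 1 are free of drug?**

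| Arm | Study drug on Day 1 | Pembrolizumab starts | Unexposed part of Cycle 1 |
|---|---|---|---|
| A | pembrolizumab, pralatrexate | Day 1 | Day 1 before dosing |
| B | decitabine, pralatrexate | Day 8 | Day 1 before dosing |
| C | decitabine | Day 8 | Day 1 before dosing |

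Days 2 to 28 number 28 − 1 = 27, so 27 of the 28 days that footnote 7 admits come after at least one study drug, in every arm. In Arms B and C, a sample from Days 2 to 7 precedes pembrolizumab but follows decitabine, and in Arm B pralatrexate too.

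**Step 3. Are the timing statements compatible?**

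| Place | Permitted time of first sample |
|---|---|
| Footnote 6 | screening phase |
| Inclusion criterion 7 | up to 42 days before treatment starts, or archived tissue if the sponsor agrees |
| Section 3.2 and Section 5.6 | before treatment |
| Footnote 7 | screening, or anywhere in Cycle 1 |

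A fresh specimen from Days 2 to 28 satisfies only the last row. Criterion 7 does not close the gap, because it tests willingness to provide tissue and does not require that the sample already exists at enrolment. The protocol states no order of precedence among these places.

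**Step 4. What happens to the paired change?** Let B be the marker before any dose, E its value in a Cycle 1 post-dose sample, and P its value after Cycle 3 or 4.

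- Intended change: Δ = P − B.
- Recorded change: P − E = Δ − (E − B).
- With f = (E − B)/Δ, recorded change = Δ(1 − f).

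If f lies between 0 and 1, the change is understated. If f exceeds 1, because the marker moved early and partly recovered, the sign reverses. If f is negative, the change is overstated. The protocol gives no time course for these markers in patients' tumours, so f is unknown.

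**The case against.** The strongest reply is that the protocol's intent is plain. The screening cell carries footnote 6, footnote 7 points to criterion 7, and the objectives speak of pre- and post-treatment tissue. On this view footnote 7 is merely loose, and its Cycle 1 option may mean Cycle 1 Day 1 before dosing. The intent is indeed clear, but that shows footnote 7 to be wrong rather than harmless. Footnote 5 names Cycle 1 Day 1 when that day is meant, and footnote 7 does not.

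Three stronger readings are tempting, and the documents do not support them.

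- *The protocol has chosen to analyse on-treatment tissue as baseline.* Nothing says so. Footnote 7 governs collection, not analysis. How samples are classed may be set out in an SAP, or in the laboratory manual cited in Section 9.1.7.3; neither is at hand. The defect is an internal contradiction about when to collect.
- *The paired results will be biased toward no effect.* That holds only when f lies between 0 and 1, which the documents do not establish.
- *Only the decitabine arms are affected.* Arm A has the same footnote and also starts drug on Day 1.

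It is also fair to say that the stakes are modest. Section 10.6 plans only graphs and exploratory repeated measures models for these markers, and nothing shows how often a site would use the Cycle 1 option. Both points stand, and they hold the matter to low priority.

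**Conclusion.** Footnote 7 contradicts footnote 6, inclusion criterion 7 and the paired pre/post objective, in all three arms. Any pair whose first sample follows the first dose fails to measure change from before treatment, and could distort the secondary pharmacodynamic and exploratory biomarker results in a direction that cannot be derived from the protocol. The number of such pairs cannot be estimated from it either.

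The conclusion rests on reading the Cycle 1 option as it is written, without an implied pre-dose limit. If the sponsor meant Day 1 before dosing, the sampling plan is sound and only the wording is at fault. The dose-finding results and the response rate do not depend on this tissue. The point is minor, but worth settling before more tissue is collected because a missed baseline cannot be replaced.

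**What to change.** In footnote 7 of the flow charts for Arms A, B and C, replace the present timing with: *at screening or on Cycle 1 Day 1 before the first dose of any study drug*. Add the same Day 1 allowance to footnote 6, so that the two footnotes agree.

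Keep the archived specimen as the fallback, with the sponsor-agreement condition of criterion 7. Add one sentence saying that tissue taken after the first dose is on-treatment tissue and is not used as the baseline of a pair.

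The change is to wording only and adds no biopsy. Two costs should be accepted openly: there may be fewer complete pairs, and archived tissue may predate intervening therapy, since criterion 7 sets no age limit on it and criterion 5 sets no cap on prior lines. Recording the date of each archived specimen and any treatment given since would let the analyst judge whether it can serve as a baseline.
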